6.6.2.1 Classifications of Adverse Events

Severity of Adverse Events:

The severity of an AE will be graded as “Mild”, “Moderate” or “Severe”. AEs events recorded with missing intensity will be summarized as Severe, following worst case principle.

Relationship to study drug/protocol procedure:

An AE will be considered as related to Flortaucipir F 18 if they occur within 48 hours after administration of Flortaucipir F 18, and will be considered as related to Florbetapir F 18 if they occur within 48 hours after administration of Florbetapir F 18.

In addition, the investigator will assess the relatedness of an AE to protocol procedure.

Any missing relationship of an AE to study drug or protocol procedure will be considered to be related for the analysis, following worst case principle.

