7.7. Adverse Events (AE)

Avid’s standards for recording and reporting adverse events (AEs) are to be followed regardless of applicable regulatory requirements that may be less stringent. All AEs must be fully recorded on the adverse event eCRFs. Investigators will be instructed to report to Avid, or its designee, their assessment of the potential relatedness of each AE to study drug or protocol procedure via electronic data entry. If a patient’s treatment is discontinued as a result of an AE, study site personnel must clearly report to Avid, or its designee, via electronic data entry the circumstances and data leading to any such discontinuation of treatment. In cases where the investigator notices an unanticipated benefit to the patient, study site personnel should report “unexpected benefit” with the actual event term to Avid, or its designee (for example, the complete actual term would be “unexpected benefit- sleeping longer”).

Laboratory test abnormalities considered by the Investigator to be clinically relevant should be reported on the adverse event eCRFs. Signs and symptoms of each AE should be described in detail (e.g., start and stop dates/time, severity/intensity, relationship to study drug, action taken, and outcome).

Protocol ¹⁸F-AV-1451-A19: “¹⁸F-AV-1451 PET Imaging in Subjects with Frontotemporal Dementia”

Additionally, any clinically significant findings from laboratory evaluations, vital sign measurements, or other study procedures including those that result in a diagnosis should be reported as an AE to Avid, or its designee.

7.7.1. *Adverse Event Monitoring*

Each patient must be carefully monitored for adverse events. This includes clinical laboratory test variables. An assessment must be made of the severity/intensity and relationship to the administration of the study drug.

7.7.2. *Adverse Event Definitions*
Adverse Events

An adverse event is any undesirable experience occurring to a subject during a clinical trial, whether or not considered related to the study drug.

For reporting purposes, Avid will distinguish among pre-existing conditions, trial-emergent adverse events and treatment-emergent adverse events.

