Pre-existing conditions (i.e., undesirable experiences, signs or symptoms that begin prior to the Screening Visit) will be recorded on the medical history eCRF pages. During the study, site personnel will record any change in the condition(s) and occurrence and nature of any AEs. Signs and symptoms that are believed to be due to the pre-existing condition(s) (started prior to dose of study medication) do not have to be recorded in the AEs section of the eCRF, unless there is an increasing in frequency and severity. Additionally, signs or symptoms or changes in pre-existing conditions that occur outside the trial defined adverse event reporting period (e.g., between each imaging visit will be recorded in medical history).

An adverse event is any untoward medical occurrence associated with the use of a drug in humans, whether or not considered drug related. For the purposes of this study, untoward medical occurrences will be considered associated with the use of ¹⁸F-AV-1451, and thus be reported as adverse events, if they occur within 48 hours after administration of ¹⁸F-AV-1451. Untoward medical occurrences will be considered associated with the use of Florbetapir F 18 injection, if they occur within 48 hours after Florbetapir F 18 injection administration. Adverse events associated with the use of ¹⁸F-AV-1451 or Florbetapir F 18 injection will be recorded as treatment emergent relative to the respective drug. Adverse experiences that occur after administration of either drug but outside the 48 hour reporting window will not be reported unless the investigator believes they are attributable to the drug.

Trial-emergent adverse events are undesirable experiences, signs or symptoms that begin, or worsen in intensity or frequency, after the informed consent, and

Protocol ¹⁸F-AV-1451-A19: “¹⁸F-AV-1451 PET Imaging in Subjects with Frontotemporal Dementia”

prior to administration of study drug at the imaging visit. In order to capture possible adverse effects of trial participation, trial-emergent AEs will also be reported during the baseline imaging period but not during the 48 hour windows following the administration of ¹⁸F-AV-1451 or Florbetapir. These will be recorded on the adverse event pages.

The end of study, for the purpose of adverse event reporting, is defined as 48 hours after the last study drug administration.

Serious Adverse Event (SAE)

A SAE is an AE that results in one of the following outcomes or constitutes one of the following events:

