- Death;
- Initial or prolonged inpatient hospitalization (other than that required by protocol; “social hospitalization” or any hospitalization for non-medical reasons does not constitute a SAE);
- A life-threatening experience (that is, immediate risk of dying);
- Persistent or significant disability/incapacity;
- Congenital anomaly/birth defect;
- Considered significant by the investigator for any other reason.

Important medical events that may not result in death, be life-threatening, or require hospitalization may be considered serious adverse drug events when, based upon appropriate medical judgment, they may jeopardize the patient and may require medical or surgical intervention to prevent one of the outcomes listed in this definition.

Unexpected Adverse Event

An unexpected adverse event is an adverse event not previously reported or an adverse event that occurs with specificity, severity or frequency that is not consistent with the current IB.

Relationship to Study Drug

Investigators will be instructed to report their assessment of the potential relatedness of each adverse event to protocol procedure or study drug. The assessment of the relationship of an adverse event to the administration of the study drug is a clinical decision based on all available information at the time of the completion of the eCRF.

Intensity/Severity of an Adverse Event

Protocol ¹⁸F-AV-1451-A19: “¹⁸F-AV-1451 PET Imaging in Subjects with Frontotemporal Dementia”

In addition to assessing the relationship of the administration of the study drug to adverse events, an assessment is required, in order to determine the intensity (severity) of the event.

The following classifications should be used:

Mild:

A mild adverse event is an adverse event, usually transient in nature and generally not interfering with normal activities.

Moderate:

A moderate adverse event is an adverse event that is sufficiently discomforting to interfere with normal activities.

Severe:

A severe adverse event is an adverse event that incapacitates the subject and prevents normal activities. Note that a severe event is not necessarily a serious event; nor must a serious event necessarily be severe.

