7.7.4. Reporting of Serious Adverse Events

Study site personnel must alert Eli Lilly, or its designee, of any SAE within 24 hours of their awareness of the event via a sponsor-approved method. Alerts issued via telephone are to be immediately followed with official notification on study-specific SAE forms.

Serious adverse events occurring after a subject receives a dose of study drug will be collected in the eCRF as Adverse Events until 48 hours after the dosing of the study drug, regardless of the investigator's opinion of causation. Thereafter, SAEs are not required to be reported in the eCRF as Adverse

Events unless the investigator feels the events were related to either investigational product or drug delivery system, or a protocol procedure. If the investigator does not feel the event was related to the investigational product or drug delivery system or protocol procedure, then the event should be recorded in the eCRF as Medical History for the subject. Regardless of the investigator’s assessment of relatedness or timing, all SAEs that occur after the subject receives the investigational product should be submitted to Lilly GPS for processing to determine applicability of any expedited reporting requirements..

If a patient experiences a SAE after signing informed consent, but prior to receiving study drug, the event will NOT be reported unless the investigator feels the event may have been caused by a protocol procedure. Previously planned (prior to signing the ICF) surgeries should not be reported as SAEs unless the underlying medical condition has worsened during the course of the study.

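### SAP 6.6.2.1 sets relatedness to each tracer by onset within 48 hours instead of by the investigator, and drug-attributed events starting later than 48 hours after flortaucipir reach no AE summary table

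*SAP*

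**What the plan says.** **Relatedness in the SAP.** SAP 6.6.2.1 states: "An AE will be considered as related to Flortaucipir F 18 if they occur within 48 hours after administration of Flortaucipir F 18". A parallel sentence covers florbetapir. The investigator is then given relatedness to protocol procedure only. The same section counts a missing relationship, to drug or to procedure, as related.

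**Relatedness in the protocol.** Protocol 7.7 has investigators report "their assessment of the potential relatedness of each AE to study drug or protocol procedure via electronic data entry". Under Relationship to Study Drug, section 7.7.2 says that this assessment "is a clinical decision based on all available information". Protocol 8.2.2 plans to present AEs by relationship to treatment and to summarize all patients with SAEs.

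**The 48-hour window in the protocol.** Section 7.7.2 uses it to decide what is reported and what is treatment emergent for each drug. It opens that definition with "An adverse event is any untoward medical occurrence associated with the use of a drug in humans, whether or not considered drug related". Section 7.7.4 collects SAEs in the eCRF "until 48 hours after the dosing of the study drug, regardless of the investigator's opinion of causation".

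**After 48 hours.** Protocol 7.7.2 says: "The end of study, for the purpose of adverse event reporting, is defined as 48 hours after the last study drug administration". It makes an exception, because events "outside the 48 hour reporting window will not be reported unless the investigator believes they are attributable to the drug". For later SAEs, section 7.7.4 drops eCRF reporting as AEs "unless the investigator feels the events were related to either investigational product or drug delivery system, or a protocol procedure". SAP 6.6.2 repeats the exception for drug-attributed events.

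**Tables.** SAP 6.6.2 defines TEAEs as events that occur or worsen from either injection to 48 hours after it. Trial Emergent AEs fall before florbetapir, or between the two injection sessions outside the 48-hour windows. SAP 8.10.2 limits the summary tables to TEAEs unless otherwise specified, and the only other category it specifies is Trial Emergent AEs. SAP 5.2 declares no change from the protocol's analyses.

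**The concern.** In the protocol, an event within 48 hours is associated with a tracer in a temporal sense, whether or not anyone thinks the drug caused it. The SAP turns that association into relatedness. Since the same 48 hours also define a TEAE, the Related versus Not Related split for flortaucipir carries no information beyond onset time.

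The opposite problem arises after 48 hours. The events still recorded as AEs at that point include those an investigator has attributed to the drug, and the SAP has no table for them.

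Expanding the flortaucipir safety database is the study's only secondary objective. Readers would take the two per-tracer relatedness tables as causality assessments, and the related, serious and death counts would omit late events that an investigator did attribute to the tracer. The follow-up call is made no earlier than 48 hours after injection and asks about new adverse events, so it can bring such events to light.

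**Working it through.** No sample-size or power figure is involved. The check applies the SAP's definitions to onset times and then counts displays.

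**Inputs**
- Order and spacing: florbetapir at time 0, flortaucipir at time g, with g at least 16 h (Protocol 7.1.2).
- TEAE onset windows (SAP 6.6.2): 0 to 48 h and g to g + 48 h.
- Related to flortaucipir (SAP 6.6.2.1): g to g + 48 h.
- Trial Emergent (SAP 6.6.2): before florbetapir, or between the sessions outside the windows; nothing after the flortaucipir session.

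**Step 1: can a TEAE starting after flortaucipir be Not Related to it?** It would have to start after g, lie in a TEAE window and lie outside g to g + 48. Only the florbetapir window could supply it. That window closes at 48, and 48 < g + 48 for every g > 0, so there is no such onset. A subject who used a prior amyloid scan has only the flortaucipir window, with the same result.

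Classifying onsets in 0.5 h steps for g = 16, 24, 47, 48, 72, 240 and 1440 h gave 97 of 97 post-flortaucipir TEAE onset times Related and 0 Not Related at every gap. Not Related to flortaucipir can therefore hold only TEAEs that began before that injection. When the gap is below 48 h, some onsets are Related to both tracers: 65 of the 97 grid times at 16 h, 49 at 24 h, 0 at 72 h.

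**Step 2: where does an event starting after g + 48 go?** Both TEAE windows have closed and the Trial Emergent period ended at the flortaucipir session. Of 384 grid times up to 240 h after flortaucipir, 0 were TEAEs and 0 were Trial Emergent.

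**Step 3: displays in SAP 8.10.2**

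| Display | Total | Trial Emergent | TEAE | Use tracer relatedness | Reached by a late attributed event |
|---|---|---|---|---|---|
| Overall-summary rows | 9 | 1 | 8 | 2 | 0 |
| SOC/PT tables | 10 | 1 | 9 | 2 | 0 |
| Listings | 4 | 0 | 3 | 0 | 1 (All AEs) |

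The event can also appear in the eCRF data listings (SAP 7.1) and, if raised at the call, in the telephone listing (SAP 8.10.6).

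**Step 4: size per omitted subject.** The shift in a percentage is 100/N points.
- N = 20: 100/20 = 5.0
- N = 25: 100/25 = 4.0
- N = 30: 100/30 = 3.3
- N = 40: 100/40 = 2.5

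The planned maximum enrolled is 25. N is an assumption, because the Safety Population also counts subjects who received florbetapir only.

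**Limits of the check.** It covers onsets. An AE that began earlier and worsened inside the window is a TEAE, but SAP 6.6.2.1 speaks only of occurrence, so its class is unclear. An event more than 48 h after florbetapir but before flortaucipir does reach the Trial Emergent displays. It may miss them when a subject has no flortaucipir session (an amyloid-positive screen failure, for instance), because that definition refers to the interval between two sessions.

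**The case against.** **The text may not mean what it literally says.** A rule for a missing relationship to study drug makes sense only if an assessment is recorded, and SAP 8.10.2 keeps both Related and Not Related categories. This shows that the SAP holds two possible sources and does not say which one fills the tables. It does not rescue the rule: onset within 48 hours is written as sufficient for Related, and the missing-value default can only add Related cases.

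**The protocol itself ties events in the window to the tracer, and the per-tracer tables are the only ones that separate TEAEs by tracer.** That is fair, and a TEAE can still be Not Related to florbetapir. But the protocol's link is temporal, so tables built on it should be labelled as onset tables. The separation by tracer has a use, and the fix should not lose it without notice.

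**The rule errs on the cautious side.** It does so within 48 hours, in line with the SAP's worst-case defaults. After 48 hours the effect reverses, because events actually attributed to the drug leave every count.

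**Late serious events are not lost.** Protocol 7.7.4 sends all SAEs after investigational product to the sponsor's safety group, whatever their timing or relatedness, and the All AEs listing shows those recorded as AEs. That stands, and it limits the harm. It does not change the tables or meet the statement in Protocol 8.2.2 about summarizing all patients with SAEs.

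**The worsening point is narrow.** Agreed: SAP 6.6.2 records worsening of a pre-existing condition as an AE in its own right. The conclusion does not depend on it.

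**Conclusion.** The concern holds and should be fixed. As written, SAP 6.6.2.1 replaces the investigator's judgement of relatedness to study drug with a 48-hour clock, without declaring it. None of the TEAEs that start after flortaucipir can be Not Related to it, and 2 of 9 overall rows and 2 of 10 SOC/PT tables rest on the clock. Separately, a drug-attributed event starting more than 48 hours after flortaucipir enters 0 of 9 rows, 0 of 10 tables and 0 of the 3 TEAE-restricted listings.

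How many such late events will occur is unknown. Each affected subject shifts a percentage by 4.0 points at N = 25, or 2.5 to 5.0 points for N from 40 down to 20. The conclusion assumes that SAP 6.6.2.1 is programmed as written. The study is descriptive and the listings retain the data, so the primary objective is untouched and the harm is to the safety summaries.

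**What to change.** Change the analysis text only:

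1. In SAP 6.6.2.1, take relatedness to study drug from the investigator's recorded assessment, by tracer if the eCRF holds it that way, with missing counted as related. State how an event that worsens in the window is classified.
2. Keep 48 hours as the TEAE window only.
3. In SAP 8.10.2, add one row or table, with serious and fatal events shown, for AEs and SAEs that start more than 48 hours after a tracer and that the investigator attributes to it, whether or not a flortaucipir session took place.
4. If the 48-hour rule is kept, list it in SAP 5.2 as a change from the protocol and relabel the two per-tracer tables, and the matching overall rows, as onset within 48 hours of each tracer. Such tables are also worth keeping beside the investigator-based ones if TEAEs are to stay separated by tracer.

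The cost is SAP wording and table shells. Protocol 7.7 already requires the investigator's assessment by electronic data entry. The CRF is not among the documents, so whether it records relatedness separately for each tracer must be checked first. If it does not, the per-tracer displays can only be onset tables, with investigator relatedness shown for study drug as recorded.

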6.6.3 Serum and Urine Pregnancy Test

The serum beta hCG qualitative assessment will be performed at screening for females of child bearing potential who are not surgically sterile. A serum pregnancy test may also be performed prior to injection at the imaging visits, if required.

The urine beta hCG test will be performed at the Flortaucipir F 18 imaging visit and Florbetapir F 18 imaging visit (except if screening serum pregnancy test obtained within 24 hours prior to injection) prior to injection for females of childbearing potential.

6.6.4 Other Observations Related to Safety

6.6.4.1 Vital Signs

Vital signs assessment includes measurement of pulse rate, respiratory rate, and supine blood pressure and will be taken immediately prior to injection of Flortaucipir F 18. The vital signs measurement will also be taken prior to injection of Flortaucipir F 18 and after the completion of Flortaucipir F 18 imaging prior to discharge.

The baseline assessments will be the last assessment performed prior to the injection of Flortaucipir F 18. The change from baseline at post Flortaucipir F 18 injection time point will be defined as the observed value minus the baseline value.

The weight (lightly clothed) will be measured at both the imaging visits prior to injection of Flortaucipir F 18 and Flortaucipir F 18.

Height will only be measured at Flortaucipir F 18 imaging visit prior to the injection.

6.6.4.2 Electrocardiogram (ECG)

A resting 12-lead electrocardiogram will be recorded at screening, unless an ECG was not performed within twelve months of the screening visit and is available for review.

6.7 Pharmacodynamics Parameters

No pharmacodynamics parameters will be collected during this study.

7 STATISTICAL METHODS

7.1 General Methodology

All statistical analyses will be performed using SAS® version 9.3 or higher.

The study data collected under companion protocol such as but not limited to subjects' demographic and baseline characteristics, history taking, neurological and behavioral evaluations, and MRI will be transferred to Avid for analysis purposes. Amyloid scans used for review of enrollment criteria will also be transferred to Avid if applicable.

All values will be summarized as a single group, "Frontotemporal Dementia". Data will be summarized using descriptive statistics (number of subjects [N], mean, standard deviation [SD], quartiles, median, minimum, and maximum) for continuous variables and using frequency counts and percentage for discrete variables.

For the purpose of display, the summary results will be rounded as follows:

- Min and Max: same number of decimal places as the raw data.
- Mean and Median: one more decimal place than the raw data.
- 25th and 75th Percentile: one more decimal place than the raw data.

- SD: two more decimal places than the raw data.
- Percentages will be displayed with one decimal precision. A zero count will not have the associated percentage presented on the table.

For categorical variables with missing values, a category documenting the frequency of missing values will be displayed in the summary tables.

Subject listings of all data from the eCRF as well as any derived variables will be presented.

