7. Are patients who have received a radiopharmaceutical for imaging or therapy within the past 24 hours prior to either imaging session for this study.
8. Have evidence of amyloid deposition as demonstrated by a positive florbetapir F 18 PET scan.
9. Are patients who, in the opinion of the investigator, are otherwise unsuitable for a study of this type.

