8. STATISTICAL ANALYSIS

8.1. General Statistical Considerations

All statistical analyses will be performed using SAS® version 8.2 or higher.

The study data collected under companion protocol such as but not limited to subjects’ demographic and baseline characteristics, history taking, neurological and behavioral evaluations, and MRI will be transferred to Avid for analysis purposes. Amyloid scans used for review of enrollment criteria will also be transferred to Avid if applicable.

Data will be summarized using descriptive statistics (number of subjects [N], mean, standard deviation [SD], median, quartiles, minimum, and maximum) for continuous variables and using frequency count and percentage for discrete variables. The demographic and baseline characteristics data will be summarized for all subjects in the safety population according to clinical group. Safety data will be summarized for all patients.

Subject listings of all data from the eCRFs as well as any derived variables will be presented.

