8.2. Analyses

8.2.1. Efficacy Analyses

¹⁸F-AV-1451 images will be evaluated both by qualitative visual analysis and by regional SUV_r. Descriptive statistics will be applied to describe the distribution of tau deposition as measured by ¹⁸F-AV-1451 across clinical diagnosis groups and by florbetapir PET quantitation. Mean, standard deviation, median, minimum, and maximum values will be provided for continuous variables and counts and percentages will be provided for categorical variables.

Details of analyses will be provided in statistical analysis plan (SAP).

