5.2 Changes from the Analyses Planned in the Protocol/CIP

There are no changes from the analyses planned in the Protocol/CIP at the time of preparing this SAP.

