7.8 Examination of Subgroups

No subgroup analysis will be performed.

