8 STATISTICAL ANALYSIS

8.1 Analysis Populations

The study will use following analysis populations for data summarization. Frequency count and percentage of subjects in each analysis population will be summarized.

Population	Definition	Displays
Enrolled Population	The Enrolled Population will consist of all subjects who signed informed consent and have data captured in the clinical database.	Disposition information will be summarized using the Enrolled Population.
Safety Population	The Safety Population will include all subjects who received at least one dose of Flortaucipir F 18 or Florbetapir F 18 injection.	All demographic, baseline and safety endpoints will be using the Safety Population.
ITT Population	The ITT Population will include all subjects in safety population, for whom image data are available i.e. who have a valid Flortaucipir F 18 scan assessment [SUV _r (quantitative) and/or visual reads (qualitative)].	All analyses involving imaging outcomes will be based on the ITT Population.
Per Protocol Population	The Per Protocol Population will include all subjects in ITT population who were classified on Florbetapir positive ($\alpha\beta+$) by either investigator or Avid.	All analyses involving imaging outcomes will be based on the Per Protocol Population.

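### The SAP omits the protocol's summaries of tau uptake by clinical diagnosis and by florbetapir quantitation, yet declares no change from the planned analyses

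*SAP*

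**What the plan says.** **Protocol.** Section 8.2.1 plans descriptive statistics for the distribution of tau deposition "across clinical diagnosis groups and by florbetapir PET quantitation" and refers the reader to the SAP for details. Section 8.1 says that demographic and baseline data "will be summarized for all subjects in the safety population according to clinical group".

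**SAP.** Section 7.1 states: "All values will be summarized as a single group". Section 7.8 adds: "No subgroup analysis will be performed". Visual reads (8.9.1) and SUVr (8.9.2) are summarized by analysis population. Regional SUVr by hemisphere goes to a listing (8.9.3.1). Clinical syndrome is counted in 8.6 but not crossed with any imaging result. Section 5.2 then declares: "There are no changes from the analyses planned in the Protocol/CIP at the time of preparing this SAP".

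**The concern.** The protocol names two ways of breaking down the imaging results and hands the specification to the SAP. The SAP's general rules exclude the first, and nothing in it sets up the second. That would be a legitimate decision if it were recorded and justified. Instead, the section reserved for such decisions says that nothing changed.

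At stake is descriptive content. Protocol 8.1.1 sets a sample somewhat above the usual 10 to 15 exploratory cases because FTD pathology is heterogeneous, and expects the results to support planning of later hypothesis-driven studies. A single pooled summary cannot show whether uptake differs by syndrome. The protocol's Introduction says that FTD-Tau can be predicted with high accuracy in a minority of cases, namely carriers of a MAPT mutation or a highly correlated phenotype such as PSP-Richardson's Syndrome. Pooling mixes any such subjects with the rest.

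**Working it through.** This is a comparison of texts. The plan states no figure to reproduce, because the sample size is descriptive and has no formula behind it.

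**Step 1. Match each planned breakdown to the SAP.**

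| Planned in the protocol | Nearest SAP content | Carried over? |
|---|---|---|
| Uptake by clinical diagnosis group (8.2.1) | 8.6 counts syndromes; 8.9.1 and 8.9.2 report by analysis population; 7.1 and 7.8 exclude grouping | No |
| Uptake by florbetapir quantitation (8.2.1) | Amyloid status as a categorical baseline variable (8.4); a positive/negative classification that defines the Per Protocol Population (8.1); SUVr defined for flortaucipir only (6.4.2) | No |
| Baseline data by clinical group (8.1) | 8.4 summarizes the Safety Population, pooled under 7.1 | No, if clinical group means diagnosis |

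Of the 2 breakdowns in protocol 8.2.1, the SAP carries 0. The third row is conditional because the protocol does not define the term, although diagnosis is its most natural meaning.

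**Step 2. Compare with the declaration.** At least 2 planned analyses are absent and SAP 5.2 declares none changed. The declaration is incorrect whatever the value of the displays.

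**Step 3. What remains available.** SAP 8.6 lists diagnosis, 6.4.2 lists all regional SUVr values, and 7.1 lists all eCRF data and derived variables. A reader could rebuild the by-diagnosis description one subject at a time.

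**Step 4. How large the groups would be.** Protocol 5.3.1 names behavioral-variant FTD, FTD with motor-neuron disease, two variants of primary progressive aphasia, PSP syndrome and corticobasal syndrome. Counting the aphasia variants separately gives 1 + 1 + 2 + 1 + 1 = 6. With 25 subjects (protocol 8.1.1):

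- Average group size: 25/6 = 4.2.
- Groups with more than 5 subjects need at least 6 each. Four such groups need 4 × 6 = 24, which fits; five need 5 × 6 = 30, which does not. So at least 6 − 4 = 2 groups have 5 or fewer.
- With the most even split (five groups of 4 and one of 5, 5 × 4 + 5 = 25), all six have 5 or fewer.

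**The case against.** **The by-group tables would add little.** With six syndromes, at least two groups have 5 or fewer subjects, and perhaps all do. For those a summary says no more than the individual values already listed. This stands, and it limits the gain. But small groups are a reason to record and justify a change in SAP 5.2, not to declare none. A grouping chosen after the data are seen is also open to selection.

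**The protocol synopsis mentions no grouping.** True, but it is the shorter text and does not cancel section 8.2.1.

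**The florbetapir half is weaker.** This stands. Exclusion criterion 8 removes florbetapir-positive subjects, which narrows the range. Protocol 7.1.1.1 also accepts amyloid scans up to 3 years old, so some subjects may have no quantifiable florbetapir scan. A justified omission would be acceptable.

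Stronger readings that the documents do not support:

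- *The pooling is concealed.* SAP 7.1 and 7.8 state it openly. Only the statement in 5.2 is wrong.
- *No usable groups exist.* Protocol 5.3.1 lists syndromes, assigns diagnosis to the companion study with characterization by the enrolling physician, and SAP 8.6 already tabulates by syndrome.
- *The missing breakdown is expected tau versus TDP-43.* The synopsis mentions both pathologies, but 8.2.1 promises clinical diagnosis groups. The Introduction says that behavioral-variant FTD divides equally between the two, with no reliable way to tell them apart in life.
- *The Per Protocol Population supplies the florbetapir breakdown.* It is a yes/no classification that selects subjects, not quantitation. Its definition, "all subjects in ITT population who were classified on Florbetapir positive", also conflicts with the exclusion criterion "Have evidence of amyloid deposition as demonstrated by a positive florbetapir F 18 PET scan". That is a separate defect and carries no weight here.

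**Conclusion.** The point holds. The SAP omits both breakdowns of flortaucipir uptake in protocol 8.2.1 and, on the natural reading of clinical group, the baseline breakdown in protocol 8.1. SAP 5.2 is incorrect in saying that nothing changed.

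The effect is moderate, and the SAP should be corrected. Every planned analysis is descriptive, so no test or inference is affected. A reader might infer that the primary objective is unmet or that data are lost; neither follows. The pooled summaries still describe retention in FTD and whether an AD-typical pattern appears, and the listings keep the individual values. The loss is the planned description by clinical diagnosis, for the visual read, MUBADA SUVr and the regional SUVrs named in SAP 8.9.2.

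The group sizes assume 25 subjects and six syndromes. Protocol 5.3.1 introduces its syndromes as examples, other places say approximately 25, and the Safety Population used for baseline tables can include subjects dosed only with florbetapir. The CRF and companion study may fix the categories but are not among the documents.

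**What to change.** 1. Amend SAP 7.1, 7.8, 8.4 and 8.9 to add descriptive summaries, without tests, of baseline data, visual read, MUBADA SUVr and the 8.9.2 regional SUVrs by clinical syndrome. Use the categories tabulated in SAP 8.6 and listed in protocol 5.3.1, fixed before database lock. For very small groups, show individual values ordered by syndrome; the cut-off is the sponsor's choice. While doing so, reconcile 8.9.2, which summarizes some regions, with 6.4.2, which makes MUBADA SUVr the efficacy variable and sends regional values to listings.
2. Correct SAP 5.2.
3. For florbetapir quantitation, either define the measure and present it for subjects with a quantifiable scan, giving the number who contribute, or record and justify the omission in 5.2.

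**Cost.** Items 1 and 2 are cheap: diagnosis, visual read and SUVr are already collected or derived, so the work is a category list, a set of tables and one paragraph. For item 3, recording the omission takes a sentence or two. Presenting the display costs more, because no measure is defined and some scans may not be quantifiable. The main drawback is small groups, so the tables should be labelled as descriptive only.
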